8.2 Efficacy/Immunogenicity Assessments

Not applicable

8.3 Safety Assessments

Details regarding specific safety procedures/assessments to be performed in this study are provided below. The total amount of blood to be drawn over the course of the study (from prestudy to poststudy visits), including approximate blood volumes drawn by visit and by sample type per participant, can be found in Appendix 8. The total amount of tissue to be collected during the post-challenge duodenal biopsy study, can be found in Appendix 8.

Planned time points for all safety assessments are provided in the SoA.

8.3.1 Physical Examinations

A complete physical examination will be conducted by an investigator or medically qualified designee (consistent with local requirements) as per institutional standard. Height and weight will also be measured and recorded.

A brief directed physical examination will be conducted by an investigator or medically qualified designee (consistent with local requirements) per institutional standard.

Investigators should pay special attention to clinical signs related to previous serious illnesses.

Body Mass Index (BMI)

Body Mass Index equals a person's weight in kilograms divided by height in meters squared ($BMI=kg/m^2$). Body Mass Index will be rounded to the nearest whole number according to the standard convention of 0.1-0.4 round down and 0.5-0.9 round up.

Body weight and height will be obtained with the participant's shoes off and jacket or coat removed.

8.3.2 Vital Signs

- Participants should be resting in a quiet setting without distractions in a semi-recumbent position for at least 5 minutes prior to having VS measurements obtained.
- Semi-recumbent VS assessments will include systolic and diastolic BP, HR, RR, and temperature.
- Oral or tympanic temperature will be assessed. The same method for measuring body temperature should be used throughout the study for each individual participant.
- BP and HR measurements will be assessed with a completely automated device. Manual techniques will be used only if an automated device is not available.

8.3.3 Electrocardiograms

Single 12-lead ECG will be obtained and reviewed by an investigator or medically qualified designee (consistent with local requirements) as outlined in the SoA.

Special care must be taken for proper lead placement by qualified personnel. Skin should be clean and dry prior to lead placement. Participants may need to be shaved to ensure proper lead placement. Female participants may need to remove interfering garments.

Participants should be resting in the semi-recumbent for at least 10 minutes prior to the ECG measurement during screening.

The correction formula to be used for QTc is Fredericia.

8.3.4 Clinical Safety Laboratory Assessments

Refer to Appendix 2 for the list of clinical laboratory tests to be performed and to the SoA for the timing and frequency.

- The investigator or medically qualified designee (consistent with local requirements) must review the laboratory report, document this review, and record any clinically relevant changes occurring during the study in the AE section of the case report form (CRF). The laboratory reports must be filed with the source documents. Clinically significant abnormal laboratory findings are those which are not associated with the underlying disease, unless judged by the investigator to be more severe than expected for the participant's condition.
- All protocol-required laboratory assessments, as defined in Appendix 2, must be conducted in accordance with the laboratory manual and the SoA.
- If laboratory values from nonprotocol specified laboratory assessments performed at the institution's local laboratory require a change in study participant management or are considered clinically significant by the investigator (eg, SAE or AE or dose modification), then the results must be recorded in the appropriate CRF (eg, SLAB).
- For any laboratory tests with values considered clinically significantly abnormal during participation in the study or within 14 days after the last dose of study intervention, every attempt should be made to perform repeat assessments until the values return to normal or baseline or if a new baseline is established as determined by the investigator.

8.4 Adverse Events (AEs), Serious Adverse Events (SAEs), and Other Reportable Safety Events

The definitions of an AE or SAE, as well as the method of recording, evaluating, and assessing causality of AE and SAE and the procedures for completing and transmitting AE, SAE, and other reportable safety event reports can be found in Appendix 3.

Adverse events, SAEs, and other reportable safety events will be reported by the participant (or, when appropriate, by a caregiver, surrogate, or the participant's legally authorized representative).

The investigator and any designees are responsible for detecting, documenting, and reporting events that meet the definition of an AE or SAE as well as other reportable safety events. Investigators remain responsible for following up AEs, SAEs, and other reportable safety events for outcome according to Section 8.4.3.

The investigator, who is a qualified physician, will assess events that meet the definition of an AE or SAE as well as other reportable safety events with respect to seriousness, intensity/toxicity and causality.

8.4.1 Time Period and Frequency for Collecting AE, SAE, and Other Reportable Safety Event Information

AEs, SAEs, and other reportable safety events that occur after the consent form is signed but before intervention allocation/randomization, must be reported by the investigator for randomized participants only if the event is the result of a protocol-specified intervention, including but not limited to washout or discontinuation of usual therapy, diet, placebo treatment, or a procedure.

From the time of intervention allocation/randomization through 14 days following cessation of intervention, all AEs, SAEs and other reportable safety events must be reported by the investigator.

Additionally, any SAE brought to the attention of an investigator any time outside of the time period specified in the previous paragraph also must be reported immediately to the Sponsor if the event is considered drug-related.

Investigators are not obligated to actively seek AEs or SAEs or other reportable safety events in former study participants. However, if the investigator learns of any SAE, including a death, at any time after a participant has been discharged from the study, and he/she considers the event to be reasonably related to the study intervention or study participation, the investigator must promptly notify the Sponsor.

All initial and follow-up AEs, SAEs, and other reportable safety events will be recorded and reported to the Sponsor or designee within the time frames as indicated in [\[Table 2\]](#).

Table 2 Reporting Time Periods and Time Frames for Adverse Events and Other Reportable Safety Events

Type of Event	Reporting Time Period: Consent to Randomization/Allocation	Reporting Time Period: Randomization/Allocation through Protocol-specified Follow-up Period	Reporting Time Period: After the Protocol-specified Follow-up Period	Time Frame to Report Event and Follow-up Information to Sponsor:
Nonserious Adverse Event (NSAE)	Report if: - due to protocol-specified intervention - causes exclusion - participant is receiving placebo run-in or other run-in treatment	Report all	Not required	Per data entry guidelines
Serious Adverse Event (SAE)	Report if: - due to protocol-specified intervention - causes exclusion - participant is receiving placebo run-in or other run-in treatment	Report all	Report if: - drug/vaccine related. (Follow ongoing to outcome)	Within 24 hours of learning of event
Pregnancy/Lactation Exposure	Report if: - due to intervention - causes exclusion	Report all	Previously reported – Follow to completion/termination; report outcome	Within 24 hours of learning of event
Event of Clinical Interest (require regulatory reporting)	Report if: - due to intervention - causes exclusion	Report - potential drug-induced liver injury (DILI) - require regulatory reporting	Not required	Within 24 hours of learning of event
Event of Clinical Interest (do not require regulatory reporting)	Report if: - due to intervention - causes exclusion	Report - non-DILI ECIs and those not requiring regulatory reporting	Not required	Within 5 calendar days of learning of event
Cancer	Report if: - due to intervention - causes exclusion	Report all	Not required	Within 5 calendar days of learning of event
Overdose	Report if: - receiving placebo run-in or other run-in medication	Report all	Not required	Within 24 hours of learning of event

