1.3 Schedule of Activities (SoA)

Study Period	All Panels/Periods						
	Screening	Pre-dose	Intervention			Post-study	Notes
Scheduled Day	Screening (up to -28 days)	Day 1 Pre-dose	Day 1	Day 6	Day 13	Day 14 (+/- 1 day)	Post-study (14 days after last gluten administration)
Administrative Procedures							
Informed Consent	X						
Informed Consent for Future Biomedical Research	X						
Assignment of Screening Number	X						
Participant Identification Card	X						
Inclusion/Exclusion Criteria	X	X					Recheck clinical status before start of gluten challenge
Medical History	X						Includes usage of drugs, alcohol, and tobacco
Prior/Concomitant Medication Review	X	X	X	X		X	
Assignment of Treatment/Randomization Number		X					
Gluten Administration/Dispensing			X-----X				Gluten will be administered daily from Day 1 to Day 13. In the event that Day 14 procedures are conducted on Day 13, gluten intended for Day 13 will not be consumed.
Participant Gluten Consumption Log			X-----X				Participants will complete this log daily.
Safety Procedures							
Full physical examination	X	X			X		Pre-dose will be targeted PE
Height	X						
Weight	X	X			X	X	
Vital Signs (BP, HR, RR)	X	X			X	X	

Study Period	All Panels/Periods						
	Screening	Pre-dose	Intervention			Post-study	Notes
Scheduled Day	Screening (up to -28 days)	Day 1 Pre-dose	Day 1	Day 6	Day 13	Day 14 (+/- 1 day)	Post-study (14 days after last gluten administration)
Body Temperature	X	X				X	X
12-lead ECG	X						
Serum β -Human Chorionic Gonadotropin (β -hCG; WOCBP only)	X						
Urine β -Human Chorionic Gonadotropin (β -hCG; WOCBP only)		X				X	
Serum FSH - (postmenopausal women only)	X						
Blood for HLA Genotyping for Celiac Disease	X						Results from previous testing may be used in lieu of genotyping at screening
Anti-tTg, HIV, hepatitis B and C screen	X						
UDS	X						Screening UDS is mandatory, any additional UDS are conducted per site SOP
COVID-19 Testing	X					X	COVID-19 nasal swab test or blood test, per local practice, if deemed possible/allowed based on test capacity, and according to local health practice. Testing prior to the Day 14 duodenal biopsy may be done within 2 to 3 days prior to the procedure per the investigator's discretion. Result must be negative for duodenal biopsy to be performed.
Hematology	X					X	
Urinalysis	X					X	

Study Period	All Panels/Periods						
	Screening	Pre-dose	Intervention			Post-study	Notes

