2.3 Benefit/Risk Assessment

Participants in this clinical study will not receive direct benefit from participation.

Risks anticipated for participants in this trial are those related to the gluten challenge, venipuncture and biopsy procedures.

Additional details regarding specific benefits and risks for participants participating in this clinical study may be found in the accompanying informed consent documents.

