6 STUDY INTERVENTION

Study intervention is defined as any investigational intervention(s), marketed product(s), placebo, or medical device(s) intended to be administered to a study participant according to the study protocol.

Each participant will receive study intervention (gluten) at Visit 2 and is to take the first dose that same day. The participant should consume the intervention (gluten) daily for 13 days.

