7 DISCONTINUATION OF STUDY INTERVENTION AND PARTICIPANT WITHDRAWAL

7.1 Discontinuation of Study Intervention

Discontinuation of study intervention does not represent withdrawal from the study.

As certain data on clinical events beyond study intervention discontinuation may be important to the study, they must be collected through the participant's last scheduled follow-up, even if the participant has discontinued study intervention. Therefore, all participants who discontinue study intervention prior to completion of the protocol-specified treatment regimen will still continue to participate in the study as specified in Section 1.3 and Section 8.1.9, or if available, a protocol clarification letter.

Participants may discontinue study intervention at any time for any reason or be discontinued from the study intervention at the discretion of the investigator should any untoward effect occur. In addition, a participant may be discontinued from study intervention by the investigator or the Sponsor if study intervention is inappropriate, the study plan is violated, or for administrative and/or other safety reasons. Specific details regarding procedures to be performed at study intervention discontinuation are provided in Sections 8.1.9 and 8.11.3.

A participant must be discontinued from study intervention but continue to be monitored in the study for any of the following reasons:

- The participant or participant's legally acceptable representative requests to discontinue study intervention.
- The participant interrupts study intervention administration during Days 1 through 3 of the gluten challenge, or for more than 1 day between Day 4 through Day 13 (or Day 12 if endoscopy performed on Day 13) of the gluten challenge.
- The participant has a medical condition or personal circumstance which, in the opinion of the investigator and/or Sponsor, placed the participant at unnecessary risk from continued administration of study intervention.
- The participant has a confirmed positive serum pregnancy test.

Discontinuation from study intervention is "permanent." Once a participant is discontinued, he/she shall not be allowed to restart study intervention.

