8.1.10 Duodenal Biopsy Procedure

After completing the gluten challenge (Day 14), participants will undergo an upper endoscopy (esophagogastroduodenoscopy) with biopsies from the duodenal bulb and distal duodenum. The clinical evaluation of the participants before the procedure will be according to site standard practice. Participants will receive either conscious sedation or medically assisted anesthesia according to PI judgement. Participants will fast for at least 8 hours prior to the procedure. Up to 12 duodenal biopsies, including at least 2 from the duodenal bulb, will be collected using regular biopsy forceps. Four (4) biopsies, including at least one from the duodenal bulb, will be used for histopathological assessment, and the remainder of the biopsies will be used for additional pharmacodynamic and biomarker assessments.

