8.1.11 Discontinuation and Withdrawal

The investigator or study coordinator must notify the Sponsor when a participant has been discontinued/withdrawn from the study and/or intervention. If a participant discontinues for any reason at any time during the course of the study and/or intervention, the participant may be asked to return to the clinic (or be contacted) for a poststudy visit as per the number of days described in Section 8.11.4) to have the applicable procedures conducted. However, the investigator may decide to perform the poststudy procedures at the time of discontinuation or as soon as possible after discontinuation. If the poststudy visit occurs prior to the safety follow-up time frame as specified in Section 8.4.1, the investigator should perform a follow-up telephone call at the end of the follow-up period (Section 8.4.1) to if any AEs have occurred since the poststudy clinic visit. Any AEs that are present at the time of discontinuation/withdrawal should be followed in accordance with the safety requirements outlined in Section 8.4.

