8.11.4 Poststudy

Participants will be required to return to clinic approximately 14 days after the last dose of study intervention for the poststudy visit. If the poststudy visit occurs less than 14 days after the last dose of study intervention, a subsequent follow-up telephone call should be made at 14 days post the last dose of study intervention to determine if any AEs have occurred since the poststudy clinic visit.

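### AE collection closes 14 days after the last gluten dose whatever the biopsy date, so a participant biopsied after an early stop could have as little as 0 to 3 days of collection after the procedure

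*Combined protocol and SAP*

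**What the plan says.** The safety clock starts from gluten throughout the protocol.

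- Section 8.4.1 (AE collection): from allocation "through 14 days following cessation of intervention, all AEs, SAEs and other reportable safety events must be reported by the investigator".
- Section 6 identifies the intervention: "Each participant will receive study intervention (gluten) at Visit 2".
- The poststudy column of the Schedule of Activities (Section 1.3) is headed "Post-study (14 days after last gluten administration".
- Section 8.11.4: "Participants will be required to return to clinic approximately 14 days after the last dose of study intervention for the poststudy visit". If the visit falls earlier, a telephone call is made at 14 days after the last dose. Section 8.1.11 has a similar call at the end of the Section 8.4.1 period.

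The biopsy is treated as a risk in its own right. Section 2.3: "Risks anticipated for participants in this trial are those related to the gluten challenge, venipuncture and biopsy procedures". Section 8.1.10: "Up to 12 duodenal biopsies, including at least 2 from the duodenal bulb, will be collected using regular biopsy forceps", under sedation or anesthesia. Section 4.2.1.1 says that the safety of the procedures, as well as of gluten, will be evaluated.

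Three sections bear on participants who stop gluten early. Section 7.1 says they "will still continue to participate in the study as specified in Section 1.3", and then adds Section 8.1.9 or a protocol clarification letter. Section 8.11.3 makes their remaining procedures a subset chosen by the investigator with Sponsor agreement. Section 8.1.10 places the endoscopy after the challenge has been completed. On follow-up contact, Section 8.1.11 says only that "the participant may be asked to return to the clinic (or be contacted) for a poststudy visit".

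**The concern.** For a completer, the last gluten dose and the biopsy are 1 or 2 days apart, so it hardly matters which one starts the clock. For an early stopper they can be up to two weeks apart. Section 7.1 requires permanent discontinuation after any interruption on Days 1 to 3, or one of more than a day later on. Such a participant remains in the study, may still be biopsied around Day 14, and counts in the safety population of Section 9.5, which needs only one day of gluten.

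If that biopsy is done, the period in which sites must report events can end almost as soon as the procedure does. Beyond it, Table 2 does not require new nonserious events and asks for serious ones only if related to the drug or vaccine. Section 8.4.1 adds serious events that the investigator comes to learn of and relates to the intervention or to study participation, but it puts no duty on sites to look for them. At stake is whether procedure-related events are actively collected for a comparable time in everyone who is biopsied.

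**Working it through.** **Inputs.** AE collection ends on day L + 14, where L is the last gluten day (Section 8.4.1, with Section 6 and the Schedule of Activities). The biopsy day B is 14, and may be 13 or 15 (Section 8.11.5). If B = 13, the Day 13 gluten is not taken, so a completer then has L = 12.

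**The plan's own figure.** The synopsis gives about 8 weeks of participation: 28 days of screening + 13 of gluten + 14 of follow-up = 55 days, and 55 / 7 = 7.86 weeks. This agrees, and confirms that the 14 days are counted from the end of gluten.

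**Days of collection after the biopsy** = L + 14 − B.

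| Last gluten day L | Collection ends on day | B = 13 | B = 14 | B = 15 |
|---|---|---|---|---|
| 1 | 15 | 2 | 1 | 0 |
| 2 | 16 | 3 | 2 | 1 |
| 3 | 17 | 4 | 3 | 2 |
| 6 | 20 | 7 | 6 | 5 |
| 11 | 25 | 12 | 11 | 10 |
| 12 | 26 | 13 (completer) | 12 | 11 |
| 13 (completer) | 27 | – | 13 | 12 |

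An interruption on Days 1 to 3 that forces a stop leaves L = 1 or 2. L = 3 can arise when Days 4 and 5 are missed. Zero days requires a last dose on Day 1 and a biopsy on Day 15.

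**With the clock running from the later of the two dates.** Since B is later than L, collection ends on day B + 14, which is Day 27, 28 or 29. Every biopsied participant then has 14 days after the procedure. The extension is B − L: 1 or 2 days for completers, 12 to 14 for L = 1, 11 to 13 for L = 2 and 10 to 12 for L = 3. The longest participation becomes 28 + 29 = 57 days, or 57 / 7 = 8.1 weeks, still about 8 weeks.

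**The case against.** The strongest reply is that the protocol does not direct this biopsy. Section 7.1 allows a clarification letter to replace the schedule, Section 8.11.3 leaves procedures to case-by-case agreement, and Section 8.1.10 ties endoscopy to completing the challenge. Stoppers may be replaced (Section 5.5), and exposure over Days 1 to 13 counts towards the Per-Protocol set (Section 9.5), so there may be little reason to biopsy them. The letter could also set follow-up. This stands: the gap is conditional, and the documents give no frequency for it.

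Existing protections also count. Events already reported are followed to resolution or stabilization (Section 8.4.3), and a serious event that the investigator learns of and relates to study participation must still be notified. What is lost is active collection, chiefly of new nonserious events.

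Appendix 3 (Section 10.3.1) counts a protocol-specified procedure as study intervention, so one could argue that the window already runs from the biopsy. But that wording serves the definition of an AE, while Section 6 and the Schedule of Activities name gluten. At best the anchor is ambiguous.

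A reader might also infer four stronger points, which the documents do not support:

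- That those with the shortest follow-up tolerated the challenge worst. The Days 1 to 3 rule applies to an interruption for any reason.
- That delayed complications will be missed. The documents give no timing for biopsy complications.
- That laboratory follow-up has the same gap. Section 8.3.4 also covers abnormal values arising at any time during participation.
- That the poststudy procedures would be done before the biopsy. This combines two optional paths (Sections 8.1.11 and 8.11.3) that no section describes together.

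**Conclusion.** The point holds as a conditional gap in how AE collection is defined. No section ties the end of collection, the poststudy visit or the closing call to a procedure that the protocol names as a risk. If an early stopper is biopsied, active collection afterwards lasts 0 to 3 days in the worst case (last dose on Days 1 to 3, biopsy on Day 14 or 15), 2 to 4 days if that biopsy is on Day 13, and 5 to 7 days for a last dose on Day 6. Completers have 12 or 13.

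This assumes that cessation of intervention means the last gluten dose, that the biopsy is done after discontinuation, and that no clarification letter sets a longer follow-up. The effect on the study's results is small: this is a single-group estimation study of about 15 participants with no safety objective in Section 3. The case for changing the text is that following it as written can leave a biopsied participant almost without active AE collection, and the repair is cheap.

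**What to change.** In Section 8.4.1, define the end of AE collection as 14 days after the later of the last gluten dose and the duodenal biopsy. Where the poststudy visit falls before that date, make the existing follow-up call then. Align the Schedule of Activities header and Section 8.11.4 with this definition.

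Two further reconciliations are for the sponsor:

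- Sections 7.1, 8.1.10 and 8.11.3, on whether participants who stop gluten early are biopsied. This review takes no position on the answer.
- The optional return in Section 8.1.11, against Section 7.1, which makes data collection through the last scheduled follow-up obligatory, and Section 8.11.4, which requires the visit.

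The cost is a wording amendment with no new procedure. AE collection closes 1 or 2 days later for completers, and early stoppers who are biopsied receive a later call. The references in Section 7.1 to Section 8.1.9 (Blood Collection) for discontinuation procedures look like an editorial slip for Section 8.1.11 and can be checked in the same amendment.
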